**Table 15.1.4 13: Treated Set- COPD degree of severity (GOLD group) [grouped]**

COPD degree of severity (GOLD group) [grouped]	N	%
A/B		
C/D		
Missing		
Number of patients in Treated Set		

**Table 15.1.4 14: Treated Set- COPD degree of severity (GOLD group) – Distribution**

GOLD stadium- Distribution		A		B		C		D		Missing	
Symptoms	Exacerbations	N	%	N	%	N	%	N	%	N	%
0-1	0-1										
	>=2										
2-4	0-1										
	>=2										
Number of patients in Treated Set											

**Table 15.1.4 15: Treated Set- COPD degree of severity (GOLD group) – Smoking**

GOLD stadium- Smoking		A		B		C		D		Missing	
		N	%	N	%	N	%	N	%	N	%
Smoker											
Ex-smoker											
Non-smoker											
Missing											
Number of patients in Treated Set											

**Table 15.1.4 16: Treated Set- COPD degree of severity (GOLD group) – ICS at baseline**

GOLD stadium- ICS at baseline		A		B		C		D		Missing	
		N	%	N	%	N	%	N	%	N	%
No baseline ICS											
ICS only at baseline											
LABA+ICS at baseline											
Missing											
Number of patients in Treated Set											

**Table 15.1.4 17: Treated Set- Patients with concomitant diseases**

anamnesis.disease	N	%
Patients with concomitant diseases		
No		
Yes		
Missing		
Number of patients in Treated Set		

**Table 15.1.4 18: Treated Set- Concomitant diseases (multiple answers possible)**

Concomitant diseases	N	%
anamnesis.disease_allergic		
Allergic		
anamnesis.disease_gastro		
Gastrointestinal/Hepatobiliary		
anamnesis.disease_pulmo		
Pulmonary (except COPD)		
anamnesis.disease_reproductive		
Reproductive		
anamnesis.disease_renal		
Renal/Urogenital		
anamnesis.disease_psychic		
Psychiatric		
anamnesis.disease_neuro		
Neurologic		
anamnesis.disease_cardiac		
Cardial		
anamnesis.disease_vascular		
Vascular		
anamnesis.disease_metabolic		
Metabolic/Endocrine		
anamnesis.disease_muscular		
Muscular-skeletal/Dermatological		
anamnesis.disease_other		
Other		
Number of patients in Treated Set		

**Table 15.1.4 19: Treated Set- Concomitant diseases- Gastrointestinal/Hepatobiliary (multiple answers possible)**

Gastrointestinal/Hepatobiliary disease	N	%
anamnesis.disease_gastro_gerd		
Gastro-esophageal reflux disease (GERD)		
anamnesis.disease_gastro_other		
Other		
Patients with gastrointestinal/hepatobiliary diseases		
Number of patients in Treated Set		

**Table 15.1.4 20: Treated Set- Concomitant diseases- Pulmonary (except COPD) (multiple answers possible)**

Pulmonary (except COPD)	N	%
anamnesis.disease_pulmo_cancer		
Lung cancer		
anamnesis.disease_pulmo_other		
Other		
Patients with pulmonary diseases		
Number of patients in Treated Set		

**Table 15.1.4 21: Treated Set- Concomitant diseases- Metabolic/Endocrine (multiple answers possible)**

Metabolic/Endocrine	N	%
anamnesis.disease_metabolic_dia		
Diabetes mellitus		
anamnesis.disease_metabolic_oth		
Other		
Patients with metabolic/endocrine diseases		
Number of patients in Treated Set		

**Table 15.1.4 22: Treated Set- Concomitant diseases- Muscular-skeletal/ Dermatological (multiple answers possible)**

Muscular-skeletal/Dermatological	N	%
anamnesis.disease_muscular_osteo		
Osteoporosis		
anamnesis.disease_muscular_other		
Other		
Patients with muscular-skeletal/ dermatological diseases		
Number of patients in Treated Set		

**Table 15.1.4 23: Treated Set- Smoking**

anamnesis.smoker	N	%
Smoking		
Smoker		
Ex-smoker		
Non-smoker		
Missing		
Number of patients in Treated Set		

**Table 15.1.4 24: Treated Set- Smoking- Pack-years**

anamnesis.smoker_pack_years	N	Mean	SD	Min	Median	Max	Nmiss
Pack-years							

**Table 15.1.4 25: Treated Set- Patients with concomitant medication (except respiratory therapeutics)**

anamnesis.medication	N	%
Concomitant medication		
No		
Yes		
Missing		
Number of patients in Treated Set		

**Table 15.1.4 26: Treated Set- Diseases treated with concomitant medication (except respiratory therapeutics)- (multiple answers possible)**

anamnesis_medication.disease	N	%
Concomitant medication- Disease treated		
Allergic		
Gastrointestinal/Hepatobiliary- Gastro esophageal reflux disease (GERD)		
Gastrointestinal/Hepatobiliary- Other		
Pulmonary (except COPD)- Lung cancer		
Pulmonary (except COPD)- Other		
Reproductive		
Renal/Urogenital		
Psychiatric		
Neurologic		
Cardial		
Vascular		
Metabolic/Endocrine- Diabetes mellitus		
Metabolic/Endocrine- Other		
Muscular-skeletal/Dermatological- Osteoporosis		
Muscular-skeletal/Dermatological- Other		
Other		
Number of patients in Treated Set		

**Table 15.1.4 27: Treated Set- Concomitant medication (except respiratory therapeutics)- Continuation or new prescription (multiple answers possible)**

anamnesis_medication.type	N	%
Concomitant medication- Continuation or new prescription		
Continuation		
New prescription		
Missing		
Number of patients in Treated Set		

**Table 15.1.4 28: Treated Set- Spiolto® Respimat® - Patient trained to use inhaler**

anamnesis.spioolto_training	N	%
Patient trained to use inhaler		
No		
Yes		
Missing		
Number of patients in Treated Set		

**Table 15.1.4 29: Treated Set- Treatment with past COPD therapies (6 weeks prior to start of study treatment) according to mMRC value**

anamnesis.respiratory	mMRC value											
	Grade 0		Grade 1		Grade 2		Grade 3		Grade 4		Total	
Treatment with past COPD therapies	N	%	N	%	N	%	N	%	N	%	N	%
No												
Yes												
Missing												
Number of patients in Treated Set												

**Table 15.1.4 30: Treated Set- Treatment with past COPD therapies (6 weeks prior to start of study treatment)- Respiratory therapeutics (multiple answers possible)**

anamnesis_resp.therapy/anamnesis_resp_prescribe	Withdrawn		New		Continued		Missing	
Treatment with past COPD therapies- Therapeutics	N	%	N	%	N	%	N	%
Short-acting $\beta_2$ -Agonist								
Long-acting $\beta_2$ -Agonist								
Short-acting anticholinergic								
Long-acting anticholinergic								
Long-acting anticholinergic and long-acting $\beta_2$ -Agonist in a fixed combination								
Short-acting anticholinergic and short-acting $\beta_2$ -Agonist in a fixed combination								
Long-acting $\beta_2$ -Agonist and inhaled corticosteroid in a fixed combination								
Inhaled corticosteroid								
Systemic corticosteroid								
Theophylline								
Roflumilast (Daxas®)								
Other								
Missing								
Number of patients in Treated Set								

Visit 2 (after approx. 6 weeks of therapy)

**Table 15.1.4 31: Treated Set- Therapy with Spiolto® Respimat® carried out regularly**

visit.spioalto_regular	N	%
Therapy with Spiolto® Respimat® carried out regularly		
No		
Yes		
Missing		
Number of patients in Treated Set with visit 2		

**Table 15.1.4 32: Treated Set- Reason for therapy with Spiolto® Respimat® carried out irregularly**

visit.spioalto_regular_reason	N	%
Reason for irregular treatment		
Adverse event		
Serious adverse event		
Patient's wish		
Other		
Missing		
Number of patients with irregular treatment		

**Table 15.1.4 33: Treated Set- Changes of treatment with other COPD related therapies besides Spiolto® Respimat® since visit 1 [i.e. new therapy introduced or existing baseline therapy discontinued\*]**

visit.further_resp	N	%
Changes of treatment with other COPD related therapies		
No		
Yes		
Missing		
Number of patients in Treated Set with visit 2		

\*New therapy: New therapy in addition to already existing baseline therapies besides Spiolto® Respimat®

**Table 15.1.4 34: Treated Set- Changes of treatment with other COPD related therapies besides Spiolto® Respimat® since visit 1- Affected respiratory therapeutics (multiple answers possible)**

visit_resp.therapeutic		N	%
Changes of treatment with other COPD related therapies- Affected therapeutics			
New therapy in addition to already existing baseline therapies besides Spiolto® Respimat® introduced after visit 1	Short-acting β 2 -Agonist		
	Long-acting β 2 -Agonist		
	Short-acting anticholinergic		
	Long-acting anticholinergic		
	Long-acting anticholinergic and long-acting β 2 -Agonist in a fixed combination		
	Short-acting anticholinergic and short-acting β 2 -Agonist in a fixed combination		
	Long-acting β 2 -Agonist and inhaled corticosteroid in a fixed combination		
	Inhaled corticosteroid		
	Systemic corticosteroid		

visit_resp.therapeutic		N	%
Changes of treatment with other COPD related therapies- Affected therapeutics			
	Theophylline		
	Roflumilast (Daxas®)		
	Other		
	Number of patients in Treated Set with visit 2		
Components of existing baseline therapy at visit 1 discontinued since then	Short-acting $\beta_2$ -Agonist		
	Long-acting $\beta_2$ -Agonist		
	Short-acting anticholinergic		
	Long-acting anticholinergic		
	Long-acting anticholinergic and long-acting $\beta_2$ -Agonist in a fixed combination		
	Short-acting anticholinergic and short-acting $\beta_2$ -Agonist in a fixed combination		
	Long-acting $\beta_2$ -Agonist and inhaled corticosteroid in a fixed combination		
	Inhaled corticosteroid		
	Systemic corticosteroid		
	Theophylline		
	Roflumilast (Daxas®)		
	Other		
	Number of patients in Treated Set with visit 2		

**Table 15.1.4 35: Treated Set- Changes of concomitant diseases since visit 1 [i.e. new diagnosis or now-defunct diagnosis]**

visit.disease	N	%
Changes of concomitant diseases		
No		
Yes		
Missing		
Number of patients in Treated Set with visit 2		

**Table 15.1.4 36: Treated Set- Changes of concomitant diseases- Diseases (multiple answers possible)**

visit_disease.disease		N	%
Changes of concomitant diseases- Diseases			
A new diagnosis after visit 1	Allergic		
	Gastrointestinal/Hepatobiliary- Gastro esophageal reflux disease (GERD)		
	Gastrointestinal/Hepatobiliary- Other		
	Pulmonary (except COPD)- Lung cancer		
	Pulmonary (except COPD)- Other		
	Reproductive		
	Renal/Urogenital		
	Psychiatric		
	Neurologic		

visit_disease.disease		N	%
Changes of concomitant diseases- Diseases			
	Cardial		
	Vascular		
	Metabolic/Endocrine- Diabetes mellitus		
	Metabolic/Endocrine- Other		
	Muscular-skeletal/Dermatological- Osteoporosis		
	Muscular-skeletal/Dermatological- Other		
	Other		
	Number of patients in Treated Set with visit 2		
Existing diagnosis at visit 1 now-defunct	Allergic		
	Gastrointestinal/Hepatobiliary- Gastro esophageal reflux disease (GERD)		
	Gastrointestinal/Hepatobiliary- Other		
	Pulmonary (except COPD)- Lung cancer		
	Pulmonary (except COPD)- Other		
	Reproductive		
	Renal/Urogenital		
	Psychiatric		
	Neurologic		
	Cardial		
	Vascular		
	Metabolic/Endocrine- Diabetes mellitus		
	Metabolic/Endocrine- Other		
	Muscular-skeletal/Dermatological- Osteoporosis		
	Muscular-skeletal/Dermatological- Other		
	Other		
Number of patients in Treated Set with visit 2			

**Table 15.1.4 37: Treated Set- Changes of concomitant medication since visit 1 [i.e. new medication introduced or existing medication discontinued]**

visit.medication	N	%
Changes of concomitant medication		
No		
Yes		
Missing		
Number of patients in Treated Set with visit 2		

**Table 15.1.4 38: Treated Set- Changes of concomitant medication- Disease treated**

visit_medication.disease		N	%
Changes of concomitant medication- Disease treated			
New medication after visit 1	Allergic		
	Gastrointestinal/Hepatobiliary- Gastro esophageal reflux disease (GERD)		
	Gastrointestinal/Hepatobiliary- Other		
	Pulmonary (except COPD)- Lung cancer		
	Pulmonary (except COPD)- Other		
	Reproductive		
	Renal/Urogenital		
	Psychiatric		
	Neurologic		
	Cardial		
	Vascular		
	Metabolic/Endocrine- Diabetes mellitus		
	Metabolic/Endocrine- Other		
	Muscular-skeletal/Dermatological- Osteoporosis		
	Muscular-skeletal/Dermatological- Other		
	Other		
	Number of patients in Treated Set with visit 2		
Existing medication at visit 1 discontinued since then	Allergic		
	Gastrointestinal/Hepatobiliary- Gastro esophageal reflux disease (GERD)		
	Gastrointestinal/Hepatobiliary- Other		
	Pulmonary (except COPD)- Lung cancer		
	Pulmonary (except COPD)- Other		
	Reproductive		
	Renal/Urogenital		
	Psychiatric		
	Neurologic		
	Cardial		
	Vascular		
	Metabolic/Endocrine- Diabetes mellitus		
	Metabolic/Endocrine- Other		
	Muscular-skeletal/Dermatological- Osteoporosis		
	Muscular-skeletal/Dermatological- Other		
	Other		
	Number of patients in Treated Set with visit 2		

**Table 15.1.4 39: Treated Set- Smokers at baseline- Current status (smoking status at visit 2)**

visit.smoker	N	%
Smoker at baseline- Current status		
Patient still smokes		
Patient stopped smoking		
Missing		
Number of smokers at baseline in Treated Set with visit 2		

**Table 15.1.4 40: Treated Set- Pregnancy during treatment**

visit.pregnancy	N	%
Pregnancy during treatment		
No		
Yes		
Number of female patients in Treated Set with visit 2		

**2.2.1.1.4 15.2. Efficacy evaluation**

Primary endpoints

**Table 15.2.1 1: Full Analysis Set- Total CCQ score- Share of patients with therapeutic success after 6 weeks (approximately), defined as 0.4-point decrease of total CCQ score between baseline and week 6 (approximately)**

CCQ	N	%*	CI 95%
Share of patients with therapeutic success			
Therapy successful			
Therapy not successful			
Missing			
Total			

\*percentage is based on the total number of patients, irrespective of the availability of the CCQ score

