9.5 STUDY SIZE

We assume that patients treated with Spiolto[®] Respimat[®] will have a CCQ therapeutic success rate similar to the SGRQ responder rate. In the TONADO studies^v patients treated with Spiolto[®] Respimat[®] had a 57.5% SGRQ responder rates after 24 weeks.

The TONADO was a selected trial population, so a real world population would probably show somewhat lower numbers due to the wide diversity of potential patients that will be followed up. Therefore a 50% CCQ therapeutic success rate is a reasonable assumption.

Assuming a 50% therapeutic success rate for CCQ and a sample size of 1170 patients, the 95% confidence interval for the therapeutic success rate would be between 47.1% (lower limit) and 52.9% (upper limit).

Subgroups with long acting bronchodilators at baseline (i.e., LABA only, LAMA only, LABA and ICS) will be analyzed only if they include more than 20% of all patients. In the smallest subgroup (with at least 234 patients), assuming a 50% therapeutic success rate, the 95% confidence interval would be between 43.6% and 56.4%.

To account for a 10% drop-out rate, the sample size becomes 1300 patients.

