9.7 DATA ANALYSIS

Planned analyses

More details will be described in the statistical analysis plan (SAP).

No formal hypothesis testing will be performed since this is a self-controlled study.

All patients who have received at least one dose of Spiolto[®] Respimat[®] will be included in the analysis; this is the treated set. All analyses will be performed on the treated set (as-treated analysis). If patients have missing values for an outcome, those patients will be excluded for that outcome's analysis. For example, if a patient is missing the CCQ score at Visit 1 and/ or Visit 2, that patient will be excluded from the analyses for the primary endpoint of therapeutic success and the secondary endpoint of change in CCQs from Visit 1 to Visit 2.

The assessment will be carried out using SAS[®] software. The statistical characteristics presented in the end-of-text tables will be N / mean / SD / min / median / max for continuous

variables. Tabulations of relative and absolute frequencies will be presented for categorical variables. Incidence rates and 95% CI will be given when appropriate.

The analyses will relate to the following data:

- Patient demographics (gender, age, height, weight)
- Comorbidities (main diagnosis and concurrent diagnosis according to MedDRA, version valid as at the time of database closure)
- COPD related and other concomitant medication (according to the WHO classification, version valid at the time of database closure)
- History of smoking
- Reported exacerbations
- Breathlessness based on mMRC score at visit 1
- Therapeutic success based on CCQ score; primary outcome
- Changes from Visit1 to Visit 2 in the CCQ and CCQ-4 score; secondary outcome
- Patient satisfaction with Spiolto[®] Respimat[®] at visit 2 only; secondary outcome
- General condition of the patient: evaluated by the physician (Physician's Global Evaluation (PGE)), secondary outcome
- Willingness to continue; secondary outcome
- Adverse Drug Reactions (ADR & SADR), fatal AEs, pregnancies
- GOLD spirometric classifications (1, 2, 3, 4) and GOLD patient groups (B, C, D)
- Details of treatment with inhaled respiratory agents before the study
- Details of treatment with respiratory agents during the study
- Reasons for ending treatment during the observation period
- Details of treatment continuation / discontinuation

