**1 Methods for calculation of derived variables**

Age at registration: Year of registration {year(registration.registered\_at)} - Year of birth {patient.birthyear}

Clinical COPD Questionnaire (CCQ): Each of the 10 CCQ questions is scored by the patient on a 7-point scale between 0 (Never/Not limited at all) and 6 (Almost all the time/Totally limited or unable to do) at baseline and end of the observation after approximately 6 weeks. The (total) CCQ score measures the health and functional status. A higher CCQ score is indicative of worse status and a decrease of 0.4 points is considered to be the minimum clinically important difference (MCID). The total CCQ score and the corresponding subscales are calculated as followed, in case that at least the number of required answers is available:

Scale	Items	Items required	Scoring (For details see www.ccq.nl)	Field names
Symptom	1; 2; 5; 6	3	$\frac{\text{Sum of answered questions}}{\text{Number of answered questions}}$	ccq.q_ [01;02;05;06]
Functional state (CCQ-4)	7-10	3	$\frac{\text{Sum of answered questions}}{\text{Number of answered questions}}$	ccq.q_07- ccq.q_10
Mental state	3; 4	2	$\frac{\text{Item 3} + 4}{2}$	ccq.q_03; ccq.q_04
Total CCQ score	All subscales must be calculable		$\frac{(\text{Symptom} + \text{Functional state}) * 4 + (\text{Mental state}) * 2}{10}$	ccq.q_01- ccq.q_10

Change of CCQ score: total CCQ score at baseline minus total CCQ score after approximately 6 weeks

Therapeutic success: total CCQ score at baseline minus total CCQ score after approximately 6 weeks is greater or equal to 0.4

Non therapeutic success: total CCQ score at baseline minus total CCQ score after approximately 6 weeks is less than 0.4

Share of patients with therapeutic success: number of patients with therapeutic success divided by total number of patients

mMRC questionnaire {mmrc.activity}:

mMRC Classification	Answer
Grade 0	Breathless with strenuous exercise
Grade 1	Short of breath when hurrying on the level or walking up a slight hill
Grade 2	Walk slower than people of the same age on the level because of breathlessness, or have to stop for breath when walking at own pace on the level
Grade 3	Stop for breath after walking about 100 meters or after a few minutes on level
Grade 4	Too breathless to leave the house or breathless when dressing or undressing

GOLD group

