### 2.2 Display templates for in- or end-of-text reports

#### 2.2.1 End-of-text table templates

##### 2.2.1.1 15.1 Trial subject

##### 2.2.1.1.1 15.1.1 Disposition of subjects

Table 15.1.1 1: Disposition

	N (%)
Patients recruited {patient.id}	xx (100.0)
Patients with visit 1 {anamnesis.done}	xx (yy.y)
Reason for not performing Visit 1 {anamnesis.done_reason}	
Adverse event	xx (yy.y)
Serious adverse event	xx (yy.y)
Patient's wish	xx (yy.y)
Withdrawn consent	xx (yy.y)
Lost to follow-up	xx (yy.y)
Patient died	xx (yy.y)
Other	xx (yy.y)
Study participation not possible {patient.no_participation}	xx (yy.y)
Patients with visit 1, but no registration {anamnesis.done}{registration.registered_by}	xx (yy.y)
Patients not treated	xx (yy.y)
Patients included in Treated Set	xx (yy.y)
Patients with Visit 2 {visit.done}	xx (yy.y)
Reason for not performing Visit 2 {visit.done_reason}	
Adverse event	xx (yy.y)
Serious adverse event	xx (yy.y)
Patient's wish	xx (yy.y)
Withdrawn consent	xx (yy.y)
Lost to follow-up	xx (yy.y)
Patient died	xx (yy.y)
Other	xx (yy.y)
Patients with Visit 2- Continuation of medication after end of observation (Spiolto ® Respimat ® ) {visit.spolto_continued}	xx (yy.y)
Patients with Visit 2- Discontinuation of medication after end of observation (Spiolto ® Respimat ® )	xx (yy.y)
Reason for discontinuation of Spiolto ® Respimat ® {visit.spolto_reason}	
Adverse event	xx (yy.y)
Serious adverse event	xx (yy.y)
Patient's wish	xx (yy.y)
Withdrawn consent	xx (yy.y)
Lost to follow-up	xx (yy.y)
Patient died	xx (yy.y)
Other	xx (yy.y)

Patients included in FAS	xx (yy.y)
Reason for not included in FAS	
Available total CCQ score at visit 1 only	xx (yy.y)
Available total CCQ score at visit 2 only	xx (yy.y)
No available total CCQ score at all	xx (yy.y)
Not included in TS	xx (yy.y)

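### The primary table's footnote misdescribes its denominator, and the SAP applies a CCQ-defined Full Analysis Set to PGE, satisfaction and willingness against protocol 9.7

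*SAP*

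**What the plan says.** **Protocol.** Section 9.7 bases all analyses on the treated set (at least one dose) and removes a patient only from the analysis of the outcome that is missing. Its example is the primary outcome: "if a patient is missing the CCQ score at Visit 1 and/ or Visit 2, that patient will be excluded from the analyses" of therapeutic success and of CCQ change. Section 9.7.3 allows no imputation beyond the questionnaire's own missing-item rules. Section 9.5 states precision after drop-out: with "a sample size of 1170 patients, the 95% confidence interval for the therapeutic success rate would be between 47.1" and 52.9 per cent at an assumed 50% rate. It then adds: "To account for a 10% drop-out rate, the sample size becomes 1300 patients".

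**SAP, primary share.** Section 1 defines the share as "number of patients with therapeutic success divided by total number of patients" and names no analysis set. Table 15.2.1 1 is titled Full Analysis Set and has a row for missing. Its footnote reads: "percentage is based on the total number of patients, irrespective of the availability of the CCQ score".

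**SAP, Full Analysis Set.** The SAP gives no prose definition, and the protocol does not use the term. The content has to be inferred from the reasons for non-inclusion in Table 15.1.1 1. The first is "Available total CCQ score at visit 1 only"; the others are a score at Visit 2 only, no score at all, and not being in the Treated Set.

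**SAP, other outcomes.** Tables 15.2.1 4 (PGE), 15.2.1 5 (satisfaction) and 15.2.1 6 (willingness to continue) are also titled Full Analysis Set.

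**The concern.** Two statements about the primary percentage do not fit together. The footnote speaks of patients without a CCQ score as part of the base. The protocol excludes them, and the set named in the table's title appears to contain none. A sentence attached to the only primary outcome is therefore either redundant or contrary to the protocol, and a programmer who follows it literally could use a wider base.

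The secondary outcomes raise a separate problem. Availability of the CCQ total decides who is counted for outcomes that do not depend on the CCQ. Section 1 of the SAP requires both mental-state items for a total score. A patient who attends Visit 2, is rated by the physician and answers the satisfaction and continuation questions, but skips one of those two items, has no total score and drops out of all three tables. Protocol 9.7 would keep that patient in each of them.

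**Working it through.** **1. The plan's own figure.** Inputs from protocol 9.5: p = 0.50, n = 1170, drop-out 10%.

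- 95% CI: 0.50 ± 1.96 × √(0.25/1170) = 0.50 ± 0.0287, or 47.1% to 52.9%. This reproduces the stated interval.
- 1170/0.90 = 1300. This reproduces the planned enrolment.

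**2. Who is in the FAS.** The four reasons in Table 15.1.1 1 cover every way of lacking paired total scores, plus non-membership of the Treated Set. What remains is Treated Set patients with a total CCQ score at both visits. For the primary outcome this is the population that protocol 9.7 prescribes. The missing row of Table 15.2.1 1 must then be zero, and the footnote changes nothing.

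**3. Effect if a wider set were used.** Let N be the wider set and d the proportion of it without both scores. The successes are x = p × N × (1 − d). Over patients with scores, the share is x/[N(1 − d)] = p. Over everyone, it is x/N = p(1 − d). The shift is therefore exactly p × d. With p = 50%, x = 0.50 × 1170 = 585. The values of d above zero are assumptions.

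| Base | d | Share | 95% CI (Wald) | Shift, points |
|---|---|---|---|---|
| FAS, 585/1170 | 0 | 50.0% | 47.1 to 52.9 | 0 |
| 585/1194 | 2% | 49.0% | 46.2 to 51.8 | 1.0 |
| 585/1232 | 5% | 47.5% | 44.7 to 50.3 | 2.5 |
| 585/1300 | 10% | 45.0% | 42.3 to 47.7 | 5.0 |

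The last row needs all 1300 to be treated and the whole planned drop-out to lack paired scores. Protocol 9.5 also cites earlier studies whose patients "had a 57.5% SGRQ responder rates after 24 weeks". At that rate the shifts for d = 2, 5 and 10% are 57.5 × d = 1.2, 2.9 and 5.8 points. For scale, the planned CI half-width is 2.9 points.

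**4. PGE, satisfaction and willingness.** Among treated patients with data for one of these outcomes, let e be the proportion without paired CCQ scores. Let A be the result in those with paired scores and B the result in those without. The FAS reports A; the population in protocol 9.7 gives (1 − e)A + eB. The difference is e × (A − B). The documents give neither e nor A − B, so neither size nor direction can be stated.

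**5. The 0.4 cut (programming point).** For complete questionnaires the total score is the item sum divided by 10. Over all 57 score pairs that differ by exactly 0.4, the unrounded difference in double precision falls below 0.4 in 31. After rounding to 6 decimals it does so in none. Rounding to 1 decimal would be wrong, because section 1 of the SAP accepts three of four items in two domains. A true change of 11/30 = 0.367 is then possible, and it would round up to 0.4.

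**The case against.** The strongest reply is that the SAP already settles the primary denominator. The table's title names the FAS, the disposition table fixes its content, and where the SAP means the Treated Set it says so. Section 1 gives a generic formula whose population comes from the table that uses it. The footnote and the missing row look like leftover shell text, since missing rows recur throughout the SAP. The output would also expose any other choice: the table prints the counts for success, non-success, missing and total. All of this stands.

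A reader might infer that the primary share will be wrong by up to five points, or that the wording favours the product. The documents support neither. The shift is zero if the FAS governs, d is nowhere given, and a wider base can only lower the share. Nor is 10% a bound: it is a planned drop-out rate, scores can be missing without drop-out, and patients never treated leave the Treated Set.

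A second reply is that complete-case analysis is what protocol 9.7 prescribes, and that counting missing as non-success is an imputation that section 9.7.3 does not plan. This is right about the primary analysis. It does not rule out one row openly labelled as a sensitivity analysis.

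Neither reply covers the secondary outcomes. The base of Table 15.2.1 6, patients with Visit 2, does not help, because within the FAS that is simply everyone.

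**Conclusion.** For the primary outcome this is a wording conflict, with no numerical effect on the best-supported reading. A shift of p × d arises only if the footnote is applied literally to a wider set, and every non-zero figure for it rests on an assumed d. It is not shown that the primary estimate is wrong.

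The substantive departure is the use of a CCQ-defined set for PGE, satisfaction and willingness, where protocol 9.7 requires exclusion outcome by outcome. It drops treated patients with usable data; its size cannot be derived from the documents.

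A related gap is that every planned efficacy, sensitivity and subgroup table is titled FAS. Treated patients without paired scores appear only as disposition counts, so nothing planned shows how far complete-case exclusion might raise a single-arm success rate.

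The rounding point is a caution only. It has no effect if the program already rounds, and any effect otherwise depends on score distributions that the documents do not give.

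**What to change.** 1. State in one sentence that the FAS for CCQ outcomes is the Treated Set patients with a total CCQ score at Visit 1 and Visit 2. Use it as the denominator of the primary share and its CI. Delete the footnote and the missing row of Table 15.2.1 1, and align the definition of the share in SAP section 1. The total in Sensitivity Table 3 (section 2.3) should then equal the primary share. Tables restricted to part of the FAS, such as Sensitivity Table 12, need not match it.
2. Analyse PGE, satisfaction and willingness in Treated Set patients with data for the outcome concerned, as protocol 9.7 requires. Carry this through to Subgroup Tables 6 to 9 and Listing 15.
3. Add one row with the same numerator over the whole Treated Set, counting patients without an evaluable CCQ change as non-successes. Label it a sensitivity analysis, because protocol 9.7.3 plans no other imputation.
4. Optional: state that the cut of at least 0.4 is applied after rounding the change to about 6 decimals, not to 1 decimal.

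The cost is SAP wording, a changed population for the non-CCQ tables and one extra row; no new data are needed. The downside is that the sensitivity figure will be equal to or less favourable than the primary one.
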